#### 1.3 Hypotheses

The study will address the following hypotheses:

- 1. Children with mild to moderate chronic kidney disease secondary to structural causes have slower rates of declining GFR compared to those with acquired glomerular disease.
- Accelerated CKD progression will be associated with a positive family history of kidney disease, black race, Hispanic ethnicity, lower socioeconomic status, elevated systolic and diastolic blood pressure, high nocturnal blood pressure, anemia, periods of accelerated growth, hyperparathyroidism and hyperlipidemia.
- 3. When indicated, early surgical intervention as well as the prescription and adherence to therapy with angiotensin converting enzyme inhibitors, angiotensin receptor blockers and aldosterone inhibitors will slow CKD progression.
- 4. Systematic measurements of GFR, centrally measured "true" serum creatinine, centrally based serum Cystatin C and comprehensive clinical data will yield GFR estimating equations with better accuracy

and more precision than current formulas based on height and serum creatinine.

- 5. Declining GFR will be associated with measurable declines in neurocognitive function, behavior and quality of life in children with CKD. The greatest deficit in cognitive function will be seen in children with the longest duration of CKD, the highest stage of CKD and with the lowest hemoglobin levels.
- 6. Progressive CKD will adversely affect central nervous system conduction pathways, and detectable anatomic changes (white matter changes) will correlate with changes in neurocognitive status and GFR.
- 7. The prevalence and severity of traditional cardiovascular disease (CVD) risk factors (hypertension, hyperlipidemia) and uremia-related CVD risk factors (inflammation, malnutrition, anemia, hyperparathyroidism), will be associated with the progression of CKD.
- 8. The prevalence and severity of systemic and nocturnal hypertension will be associated with the decline of GFR and the development of concentric left ventricular hypertrophy (LVH). The prevalence and severity of anemia will be correlated with GFR decline and the development of eccentric LVH.
- 9. LVH will be responsible for decreased LV diastolic function in children with CKD.
- 10. Decreased aortic wall compliance will be related to elevated systolic blood pressure, hyperlipidemia, biomarkers of inflammation and increased Ca x P product.

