Many factors may influence the severity of cognitive deficits in children with CKD especially age of onset [Crittenden 1985, Rasbury 1986] and duration of kidney failure [Fennell, III 1984, Rasbury 1983]. Other factors, related both to kidney failure and to cognitive function may confound the association between progressive CKD and developmental dysfunction. These potential confounding factors include: anemia, recognized to be associated with delayed development in children and impaired cognitive function in adults [Halterman 2001, Lawry 1994, Marsh 1991, Sagales 1993], and depression which adversely affects attention span and memory and clearly affects both children and adults with ESRD. Careful measurement of these factors must be included in any evaluation of neurological impairment in children with CKD. This study will obtain baseline measurements of cognitive function within 6 months of the baseline GFR assessment, depending on the age of the child. In addition, this study will obtain subsequent biannual (at odd years) neuropsychological, behavioral, and psychiatric assessments on all subjects in this cohort. Quality of life will be assessed annually. To explore whether changes in GFR are associated with subsequent anatomic and structural changes in the brain, a subset of patients had further testing with Magnetic Resonance Imaging (MRI). The CKiD study is the first large-scale attempt at systematically studying the impact of renal disease on neurocognitive function in children. This study will yield much needed information on the impact of renal disease on neurocognitive function and will serve to characterize the impact of chronic kidney disease on quality of life.

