Currently available data on echocardiographic parameters in children with CKD are from small, single-center cross-sectional studies. We will obtain ECHO measurements in the entire cohort because there is a lack of published data establishing normative findings in children with CKD. Justification for ECHO measurement in the entire cohort, the proposed time sequence and hypotheses are based on important findings reported in preliminary studies by CKiD investigators. This includes cross-sectional studies of children with CKD which report an association between severity of kidney disease and LVM index [Mitsnefes 2003c], hypertension/abnormal diurnal blood pressure pattern and LVH [Mitsnefes 2003b], LV diastolic dysfunction and LVH [Mitsnefes 2004a]. Expected findings in cross sectional analyses in CKiD are for an association between blood pressure (or a diagnosis of hypertension) and the presence of concentric LVH; those with decreased hemoglobin will have eccentric LVH. We hypothesize that LVM index will significantly correlate with SBP, and inversely correlate with hemoglobin level and GFR level. In prospective analyses, we hypothesize that changes in LVM index over time will be related to changes in SBP, hemoglobin concentration and GFR. It is expected that there will be an association between the prevalence of LV diastolic dysfunction and kidney disease severity in children with CKD. Indices of decreased LV relaxation and LV compliance (from tissue Doppler) will significantly correlate with increased LVM, high BP and increased Ca x P product/iPTH level. In children who develop LVH over time, increased LVM index will be associated with worsening of diastolic function.

To ensure adequate statistical power to determine the prevalence and progression of CV abnormalities over time, we will need to perform the CV tests on approximately 600

children in Cohort 1 who are expected to be seen at the second visit when the CVD protocol will be implemented. Based on prior work by [Johnstone 1996, Mitsnefes 2003c], we expect between 20% and 30% of the children to have prevalent CV abnormalities (specifically LVH) at baseline. Table 6.4.1.3 illustrates the statistical power for the prevalence ratio of CV abnormalities varying the size of the

Table 6.4.1.3 Detectable Prevalence Ratios for	
CV abnormalities among 510 children	
with a 2-sided alpha of 5% and power of 80%	

	Percent exposed:		
Overall Prevalence:	10%	30%	
20%	1.95	1.66	
30%	1.69	1.47	

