The above regression will be extended to control for possible confounding by age since diagnosis and socioeconomic status by the addition of  $b_4A_{ij}$  and  $b_5SES_{ij}$ , where  $A_{ij}$  is the percent of a child's age that the child has lived with CKD centered about 50% (= [100(t - age of diagnosis of CKD) / t ] - 50) and SESij is the socioeconomic status measured by family income and/or parental educational achievement (For more detail regarding the specification of Age please see section 8.2.1). Here  $b_4$  is quantifies the shift of the regression line for a one percent increase in age since CKD diagnosis. The parameter  $b_5$  quantifies the effect of a 1-unit increase socioeconomic status on the shift of the regression line. In this extended model, the slope  $b_1 + b_3$  estimates the effect of a decline of 5 ml/min|1.73m^2 of GFR, independent of age at diagnosis and socioeconomic status. To explore potential effect modification, the above extended model will be stratified by the presence of psychiatric diagnoses (e.g. ADHD).

In addition to general cognitive functioning as measured by IQ, the Neurocognitive Subcommittee is interested in exploring overall achievement, adaptive and social behavior, and measures of attention.

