The above regression will be extended to control for possible confounding by age since diagnosis, blood pressure and body mass index by the addition of +  $b_4A_i + b_5SBP_i + b_6BMI_i$ , where  $A_i$  is the percent of a child's age that the child has lived with CKD centered about 50% (= [100(t – age of diagnosis of CKD) / t ] – 50), SBP\_i is the average of two clinical systolic blood pressure measurements, and BMI\_i is the child's body mass index. Here  $b_4$  is quantifies the shift of the regression line for a one percent increase in age since CKD diagnosis. For example, in children 12 years of age, those who have had CKD since age 9 versus those who have had CKD since age 6 will differ in Y12 by  $b_4[100x(6/12 - 3/12)]= 25b_4$ . The parameters  $b_5$  and  $b_6$  quantify the effects of a 1-unit increase in systolic blood pressure and body mass index on the shift of the regression line, respectively. In this extended model,  $b_3$  estimates the effect of a decline of 5 ml/min[1.73m^2 of GFR, adjusting for age at diagnosis, systolic blood pressure, and body mass index.

To explore potential effect modification, the above extended regression model will be stratified by the use of ACE inhibitors and/or quintiles of sodium intake, as measured with a food frequency questionnaire, to assess whether the effect of GFR decline on change in LV thickness differs in the presence of this therapy or salt intake.

Of course, more detailed analysis plans and further delineated analytic models will be possible as data accumulates and hypotheses develop. For instance, the Cardiovascular Subcommittee has expressed interest in the analysis of repeated measurements of clinical blood pressures as well as episodes of nocturnal 'dipping' blood pressure available from ambulatory blood pressure monitoring.

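### The extended IQ and LV mass index models leave out hemoglobin, so their GFR-decline coefficients may include an anemia effect

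*Protocol*

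**What the plan says.** Section 8.2 sets out regressions of an outcome on recent GFR decline, then an extended version of each.

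- IQ (8.2.1): the model "will be extended to control for possible confounding by age since diagnosis and socioeconomic status". The two added terms are the percent of the child's life lived with CKD and SES. The resulting GFR-decline effect is described as "independent of age at diagnosis and socioeconomic status". The extended model is then stratified by psychiatric diagnoses.
- LV mass index (8.2.2): the model "will be extended to control for possible confounding by age since diagnosis, blood pressure and body mass index". Time between echocardiograms and baseline LV are already in it. It is then stratified by ACE inhibitor use and/or sodium intake.

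Elsewhere the protocol gives hemoglobin a part in both outcomes.

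- Section 2.2, on cognition: "These potential confounding factors include: anemia, recognized to be associated with delayed development in children and impaired cognitive function in adults". It adds: "Careful measurement of these factors must be included in any evaluation of neurological impairment in children with CKD".
- Hypothesis 5 expects the greatest cognitive deficit with the longest CKD duration, "the highest stage of CKD and with the lowest hemoglobin levels".
- Hypothesis 8: "The prevalence and severity of anemia will be correlated with GFR decline and the development of eccentric LVH".
- Section 6.4.1.3 expects that "changes in LVM index over time will be related to changes in SBP, hemoglobin concentration and GFR".

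Hemoglobin comes from the local blood count, done every year (6.2.1.9) in the whole cohort (6.4.1.4.1).

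**The concern.** Both extended models are written for the purpose of controlling confounding, and each fixes its list of added terms. A factor that the protocol itself ties to the outcome and to GFR decline is in neither list, as covariate or as stratifier. If children with lower hemoglobin also lose GFR faster, and lower hemoglobin goes with lower IQ or higher LV mass index, part of the hemoglobin association will appear in the GFR-decline coefficient.

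The direction is unhelpful in both cases. GFR decline is coded positive, so its correlation with hemoglobin would be negative. Multiplied by a positive hemoglobin effect on IQ, this lowers the IQ coefficient. Multiplied by a negative hemoglobin effect on LV mass index, it raises that coefficient. Both shifts are towards the harm that the study expects to find.

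The treatment is also uneven. Section 6.4.1.3 names systolic pressure, hemoglobin and GFR together. The LV model keeps the first and third and drops the second, with no reason given.

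**Working it through.** **Text check.** The covariate lists, term by term:

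| Model | Terms besides GFR decline | Hemoglobin |
|---|---|---|
| IQ, extended (8.2.1) | time, time by GFR decline, percent of life with CKD, SES | absent |
| LV mass index, extended (8.2.2) | time between echocardiograms, baseline LV, percent of life with CKD, systolic pressure, BMI | absent |

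The propensity-score, weighting and marginal structural methods in 8.1.1 are described in general terms and are not assigned to hemoglobin in either analysis.

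**Size.** The protocol states no figure for this, so there is none to reproduce. Inputs:

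- N of about 300 for the LV analysis (8.2.2). No N is stated for the IQ model.
- r, the absolute correlation of hemoglobin with GFR decline given the other covariates: assumed 0.1 to 0.3.
- b, the absolute effect of hemoglobin on the outcome, in SD per SD: assumed 0.1 to 0.3.

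With hemoglobin omitted and no direct GFR effect:

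- shift in the GFR-decline coefficient = r × b
- SE = √(1 − shift²) / √N
- z = shift / SE
- chance of a significant result (two-sided 5%) = Φ(z − 1.96) + Φ(−z − 1.96)

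| r | b | shift (SD) | SE | z | chance of significance |
|---|---|---|---|---|---|
| 0.1 | 0.1 | 0.01 | 0.058 | 0.17 | 5.3% |
| 0.2 | 0.2 | 0.04 | 0.058 | 0.69 | 10.7% |
| 0.3 | 0.2 | 0.06 | 0.058 | 1.04 | 18.0% |
| 0.3 | 0.3 | 0.09 | 0.057 | 1.56 | 34.7% |

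A simulation with r = b = 0.3 gave a coefficient of 0.09 with hemoglobin omitted and 0.00 with it included. The same pair (0.09 and 0.00) appeared when hemoglobin was generated as a consequence of GFR decline instead of a common cause. The data alone therefore do not separate confounding from mediation. The timing of the hemoglobin measurement has to do that.

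These figures apply to a single coefficient, as in the LV model. In the IQ model GFR decline enters both as a main effect and multiplied by time, so there the calculation indicates only the mechanism.

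**The case against.** Several points on the other side are sound and limit the claim.

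- **Examples, not a full plan.** Section 8.2 is headed as examples, and 8.2.2 expects more detailed models later. A reader might infer that hemoglobin will never be adjusted for. The documents do not say that. The flaw is in the two models as written, whose added terms are stated definitely.
- **What section 2.2 requires.** A reader might take it to demand a regression term for anemia and depression. Its wording governs careful measurement, which the yearly blood count and the BASC scales provide. Naming anemia as a possible confounder still argues for adjustment.
- **No over-claim.** A reader might infer that the protocol presents these estimates as free of confounding. It does not: each is described as adjusted for its listed terms only.
- **Anemia may be a consequence.** The background links kidney failure to reduced red cell production, Hypothesis 7 calls anemia uremia-related, and 6.2.1.3.3 regresses hemoglobin on GFR. To that extent, leaving it out gives a legitimate total effect. But Hypothesis 2 associates anemia with faster progression, so the structure is mixed. Blood pressure has the same dual position (Hypotheses 2 and 8), and 8.2.2 adjusts for it.
- **Other analyses.** A reader might infer that the hemoglobin parts of Hypotheses 5 and 8 go untested. Section 8.2 covers only effects of GFR decline, and 6.4.1.3 describes hemoglobin analyses for LV mass index, so this does not follow.
- **Strength of the link.** Calling hemoglobin a driver of LV mass would go too far; the protocol speaks of correlation and relation.
- **Proxy for GFR level.** Hemoglobin at the start of the interval partly reflects GFR at that time, which neither model contains. Baseline LV may also already absorb some earlier anemia effect.

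**Conclusion.** The omission is real and worth correcting, as a gap between two stated adjustment lists and the protocol's own account of hemoglobin. The GFR-decline coefficients may include an anemia effect; whether and how far they do cannot be settled from the documents.

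Under the assumed range the shift is 0.01 to 0.09 SD, and at about 300 children the chance of a significant result under a null GFR effect is about 5% to 35%. At the low end this is practically the nominal rate. These figures rest on assumed values of r and b, a normal approximation, and reading hemoglobin as a confounder. To the extent it is a mediator, the shift is part of the total effect and not an error.

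A reader might use the 508 children with repeated GFR in section 9.1 (99 + 409), which would give up to about 53%. That number does not belong to the LV model, which 8.2.2 restricts to about 300.

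**What to change.** In 8.2.1 and 8.2.2, add to the extended model hemoglobin from the visit that supplies the first GFR value of the decline term (visit j−1 in the protocol's notation for that term). Measured there, it precedes that interval's decline and cannot be its result. Report the GFR-decline estimate with and without hemoglobin, and label the estimate without it as including any pathway through anemia.

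A BASC depression term in the IQ model is optional, because that model is already stratified by psychiatric diagnoses.

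The cost is analysis wording and one additional fit per model; the yearly blood count already supplies the data. The downside is that hemoglobin at that visit partly reflects earlier GFR loss, so the adjusted estimate may be conservative. Reporting both estimates lets the reader see this.

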# 8.2.1 Intelligence Quotient

The intelligence quotient (IQ) is a general and stable indicator of general cognitive functioning that will be validly and reliably measured on children 30 months and older in CKiD. Let  $Y_{ij}$  be the IQ as derived from the WPPSI-III for children aged 30 months to 5 years, or the WASI for children aged 6 to 18 years for child i at visit j, where visit j is taken at time t.

A regression of the form  $Y_{ij} = b_0 + b_1t_{ij} + b_2G_{ij} + b_3G_{ij}t_{ij}$ , where the variable  $G_{ij}$  is the decline of GFR in the preceding year scaled to a 5-unit difference (= (GFRij-1 – GFRij)/5), will describe the trajectory of cognitive functioning as a line with intercepts  $b_0$  for those with no GFR decline and  $b_0 + b_2$  for those with a 5 ml/min|1.73m^2 decline in GFR, and slopes  $b_1$  for individuals who have no GFR decline and  $b_1 + b_3$  for those with a 5 ml/min|1.73m^2 decline in GFR. Here, the intercepts describe the initial difference in IQ due to decline in GFR, and the slopes describe the linear rate of change in IQ due to decline in GFR. Since this study is planning to measure GFR every two years, we will CKiD Protocol 91 06/01/16 to 08/01/17 OSMB Approved

either annualize the change in GFR over the preceding two years for which the observed data will be available or we will estimate the GFR not measured directly in a given year using the serum creatinine which will be available every year. Specifications other than the annual difference in GFR will be explored. Also, we will be able to investigate nonlinear changes in IQ over time by a polynomial expansion of tij into say the cubic function  $t_{ij} + t^{2}_{ij} + t^{3}_{ij}$ . The intrinsic statistical dependence of repeated IQ measurements taken on individuals will either be included as additional parameters using mixed effects models or will be treated as a nuisance using generalized estimating equations.

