### 8.2.2 Left Ventricular Thickness

One key outcome for the cardiovascular aim is change in left ventricular (LV) thickness, as measured by echocardiogram at the visit 2 and every other year thereafter. LV thickness will be quantified as the LV mass index in units of g/m2.7. We will also explore use of interventricular and posterior wall thicknesses, but constrain ourselves here to LV mass index. Due to the timing of the echocardiography, we will have approximately 300 children with two measurements of LV thickness during the 1st funding cycle: the analysis described below is restricted to these approximately 300 children.

Let Yi be the 2-year change in LV thickness measured in units of  $g/m^{2.7}$  for child i (= yij - yij-2). We will fit a regression model for the effect of decline in GFR on the change in LV thickness of the form Yi = b0 + b1ti + b2LVi + b3Gi, where ti measures the time between the two echocardiograms, centered at 2 years (= (tij - tij-2) - 2), the variable LVi measures the baseline LV thickness, centered at its mean, and Gi is the decline of GFR in the year preceding the baseline LV measurement scaled to a 5-unit difference (= (GFRij-1 - GFRij)/5). This model will describe the average change in LV thickness as b0 for those with 2 years between echocardiograms, average LV thickness at baseline, and no GFR decline. Individuals with 2-years between echocardiograms and average baseline LV thickness who exhibit a GFR decline of 5 ml/min|1.73m^2 will have an

average change in LV thickness of  $b_0 + b_3$ , such that  $b_3$  quantifies the effect of GFR decline on change in LV thickness.

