The above regression will be extended to control for possible confounding by age since diagnosis and caloric intake by the addition of  $b_4A_{ij}$  and  $b_5C_{ij}$ , where  $A_{ij}$  is the percent of a child's age that the child has lived with CKD centered about 50% (= [100(t – age of diagnosis of CKD) / t ] – 50) and Cij is the caloric and/or protein intake measured by Food Frequency Questionnaire. Here  $b_4$  quantifies the shift of the regression line for a one percent increase in age since CKD diagnosis. The parameter  $b_5$  quantifies the effect of a 1-unit increase in caloric and/or protein intake on the shift of the regression line. In this extended model, the slope  $b_1 + b_3$  estimates the effect of a decline of 5 ml/min|1.73m^2 of GFR, independent of age at diagnosis and caloric intake.

To explore potential effect modification, the above extended model will be stratified by the use of growth hormone and/or steroids to assess whether the effect of GFR decline differs in the presence of these therapies.

In addition to linear growth, we will explore changes in body mass and specific biomarkers, such as iPTH over the course of follow up.

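### The example IQ and height models name b1 + b3 as the effect of GFR decline, but b1 + b3 is the time slope among children who decline; the effect is b3 on slope and b2 + b3·t on level

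*Protocol*

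**What the plan says.** Section 8.2 offers worked examples of aim-specific analyses. For IQ (8.2.1) the outcome is regressed on time t, on G and on their product: Y = b0 + b1·t + b2·G + b3·G·t. G "is the decline of GFR in the preceding year scaled to a 5-unit difference", so G = 0 is no decline and G = 1 is a decline of 5 ml/min|1.73m2. The section labels b1 as the slope when GFR has not fallen, and b1 + b3 as the slope when it has fallen by 5 units. The same paragraph is looser elsewhere. It ties the gap between the two intercepts to GFR decline, which is right, but it treats the slopes themselves in the same way: "the slopes describe the linear rate of change in IQ due to decline in GFR".

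The extended model adds b4·A (percentage of life lived with CKD) and b5·SES. Of the sum b1 + b3 the text then says that it "estimates the effect of a decline of 5 ml/min|1.73m 2 of GFR, independent of age at diagnosis and socioeconomic status".

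Section 8.2.3 repeats the structure for height SDS, with caloric or protein intake in place of SES. It again presents b1 + b3 as the effect of a 5-unit decline "of GFR, independent of age at diagnosis and caloric intake".

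Section 8.2.2 (left ventricular thickness) has no time interaction. There b0 is the mean change without decline, b0 + b3 the mean change with a 5-unit decline, and b3, the coefficient of G, is what "quantifies the effect of GFR decline on change in LV thickness".

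**The concern.** A slope in one group is not an effect; the effect is the difference between that slope and the slope in the comparison group. By naming b1 + b3, sections 8.2.1 and 8.2.3 credit to GFR decline whatever drift over time is seen in children whose GFR did not decline.

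The protocol gives no ground for taking that drift as zero. It fits b1 as a free parameter. Section 6.3.3 allows that a persistently low GFR may harm cognition without further decline. Section 5.4.1 recognises practice learning. Section 8.2.1 changes the IQ instrument at age 6, and section 2.4 reports faster growth under growth hormone. Any of these could move b1.

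The stratified analyses inherit the problem. Section 8.2.3 stratifies by growth hormone and/or steroid use, and 8.2.1 by psychiatric diagnosis, to see whether the effect of decline differs. If b1 differs between strata and b3 does not, comparing b1 + b3 would show effect modification that is not there.

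These are the protocol's only worked models for the neurocognitive and growth aims, so an analyst who follows the text literally would report the wrong quantity for both.

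**Working it through.** **Inputs.** The model, the definition of G and the reading of the two slopes come from 8.2.1 and 8.2.3. Section 8.2 gives no alpha, SD, sample size or expected trend for these models, so there is no stated figure to reproduce and the check is algebraic.

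**Step 1: slopes.** From Y = b0 + b1·t + b2·G + b3·G·t, the slope in t is b1 + b3·G.
- At G = 0 the slope is b1.
- At G = 1 the slope is b1 + b3.

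Both agree with the protocol's own labels.

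**Step 2: effect on the rate of change.** Slope(G = 1) − slope(G = 0) = (b1 + b3) − b1 = **b3**.

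**Step 3: effect on level at time t.** Y(t, G = 1) − Y(t, G = 0) = **b2 + b3·t**. This holds whether t is time on study or age.

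**Step 4: added covariates.** The terms b4·A and b5·SES (or b5 times intake) do not involve G. They cancel from both contrasts, so the extended model does not turn b1 + b3 into the effect.

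**Step 5: error in the named quantity.** (b1 + b3) − b3 = b1. It is zero only if children without decline have no time trend.

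**Numerical check with illustrative values** b1 = −0.5, b2 = −1.0, b3 = −0.3:
- slope at G = 0: −0.5; slope at G = 1: −0.5 − 0.3 = −0.8
- effect on slope: −0.8 − (−0.5) = −0.3, whereas the protocol's named quantity is −0.8
- effect on level: −1.0 at t = 0; −1.0 − 0.3 × 2 = −1.6 at t = 2; −1.0 − 0.3 × 5 = −2.5 at t = 5

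**Strata, also illustrative.** Let b3 = −0.3 in both strata, with b1 = −0.5 in one and 0 in the other. Then b1 + b3 is −0.8 and −0.3. The gap of 0.5 is entirely the difference in b1.

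**Illustration by simulation.** All inputs are assumptions: 400 children, visits at 0, 2, 4 and 6 years, between-child SD 12, residual SD 6, G normal with mean 0.5 and SD 1, cluster-robust standard errors, two-sided 5%, 1,000 runs per setting. Ranges span G varying by visit and G fixed per child. Entries are rejection rates.

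| Truth | b1 + b3 | b3 | b2 and b3 jointly |
|---|---|---|---|
| b1 = −0.5, b2 = b3 = 0 (trend, no GFR effect) | 99.9–100% | 4.6–5.3% | 4.6–4.7% |
| b1 = +0.5, b2 = 0, b3 = −0.5 (effect cancelled by trend) | 4.3–5.3% | 91.7–100% | 99.9–100% |
| b1 = b3 = 0, b2 = −2 (effect on level only) | 4.4–5.5% | 4.9–6.3% | 82.6–100% |
| all zero | 5.1–6.0% | 4.8–5.0% | 4.8–4.9% |

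The third row shows why b2 belongs in the inference: an effect on level alone is invisible to both b1 + b3 and b3.

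**The case against.** The best defence is that this is a slip of interpretation. The equation contains b2 and b3 and estimates both whatever the prose calls them. The first paragraph of 8.2.1 labels the two slopes correctly, and 8.2.2 names the right coefficient for its model. Section 8.2 is headed as examples, and 8.2.2 says fuller analysis plans will follow as data accumulate. No test of b1 + b3, decision rule, alpha or sample size is stated. Both outcomes are age-normed, 8.2.1 calls IQ stable, and 5.4.1 expects the two-year spacing to limit practice learning, so b1 may be small.

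Most of this stands, and it limits the weight of the point. It does not make the sentences right. A small b1 is a hope that the protocol never states as an assumption, and nowhere do the IQ or height sections name b3, or b2 + b3·t, as the effect.

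Two stronger readings are tempting, and the document supports neither.
- **Error rates.** A reader might infer that the study will declare false effects at rates like those in the table. With no stated test and no stated b1, SD or sample size for these models, those rates only illustrate the direction of error.
- **Baseline.** A reader might infer that the baseline IQ or height drops out because G needs an earlier GFR than the first study measurement. The protocol does not say so. Section 8.2.1 allows creatinine-estimated GFR and other specifications of the exposure, and Cohorts 1 and 2 have two eligibility estimates of GFR. Redefining G as cumulative decline would change the question asked and is not needed here.

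**Conclusion.** The point holds as an error in which parameter is named as the effect, in both 8.2.1 and 8.2.3. On the protocol's own definitions, a 5 ml/min|1.73m2 decline changes the rate of change by b3 and the level at time t by b2 + b3·t. Reporting b1 + b3 overstates, understates or hides the slope effect by exactly b1. It can also produce false effect modification across the growth-hormone, steroid or psychiatric strata.

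The algebra rests on no assumption beyond the written model. The practical size depends on b1, which the document does not give: if b1 is 0 there is no error, and if b1 = −b3 a real effect on slope disappears. The model itself is sound. The wording should be corrected because it would misdirect anyone who reports from it.

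**What to change.** In the extended-model paragraphs of 8.2.1 and 8.2.3, replace the statement about b1 + b3 with wording such as: *b3 estimates the effect of a 5 ml/min|1.73m2 decline in GFR on the rate of change of the outcome, and b2 + b3·t its effect on the level at time t, adjusted for the listed covariates.*

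Align the looser sentences in the base-model paragraphs of both sections. The slopes b1 and b1 + b3 describe change over time in children without and with the decline; only their difference, b3, relates to the decline. Likewise the difference between the two intercepts is b2.

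State that reporting uses these contrasts, that inference on any association takes b2 and b3 jointly, and that strata are compared on b2 and b3 and not on b1 + b3. Section 8.2.2 needs no change on this point.

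The cost is a few sentences in two sections. The fitted model, visit schedule, data collection and sample size are unaffected.
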